### ***Time to Events***

Secondary time to event outcome measures include time to ICU discharge, time on invasive mechanical ventilation (subgroup analysis), time on non-invasive ventilation (subgroup analysis), time to discharge alive, and time to resolution of organ failure through Day 28. In addition, the Day 28 estimate from each lifetable will be analyzed. These endpoints will be displayed and analyzed in the same way as the time to respiratory failure resolution. Any deaths irrespective of an event (all favorable) or withdrawals without the event will be counted as failures at Day 28; only documented events will be counted as success in the distribution construction; this conservative approach is consistent with what was done for remdesivir. Imputing Day 28 failure aligns the cumulative distribution curve with the cumulative event days.

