The other time to (favorable) event outcomes will also be assessed using cumulative distributions through Day 28 with an additional evaluation at Day 28; these outcomes include the time to ICU discharge, time on invasive mechanical ventilation, time on non-invasive ventilation, time to discharge alive, and time to resolution of organ failure. These endpoints will be analyzed and displayed the same way as the time to respiratory failure resolution with the exception of just through Day 28. Two-sided 95% confidence intervals will be displayed for the Day 28 success rate differences in the same manner as for the key secondary efficacy endpoint. Any deaths or placement on ECMO on or before Day 28, irrespective of an earlier favorable event, or withdrawals without the favorable event ever occurring will be counted as failures at Day 28; only documented favorable events will be counted as success in the distribution construction and the denominator will include all mITT patient per treatment group. The Day 28 failure imputation allows the cumulative distribution to align with the calculation of mean days saved; thus, patients withdrawing earlier than Day 28 or not reaching a favorable event by Day 28 will be counted as failures at Day 28 in the construction of the time to event lifetables; this is consistent with how favorable events were handled for remdesivir. See Sections 13.3-4 for the handling of intercurrent events and dropouts.

The mean NIAID score will further be displayed over time. The area under the curve will also be calculated and compared using an unpaired t-test. Patients dying prior to Day 28 (then Day 60) will be carried through Day 28 (then Day 60) as being dead (NIAID=1).

The NIAID score will further be assessed for the change from baseline to Day 28/exit and then to Day 60/exit. A mixed model repeated measures (MMRM) containing the same covariates as the primary efficacy endpoint will be performed to explore the impact of modeling serial data; an unstructured covariance symmetry will be assumed; in the event that the unstructured covariance structure does not converge, then an autoregressive (1) structure will be tried, and if that does not work, then a Toeplitz structure will be tried.

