#### Key Secondary Measure:

- 2) NIAID Ordinal Scale for Clinical Improvement reaches NIAID Score 6-8 by Day 28/exit (primary); percent achieving a NIAID Score 6-8 will be evaluated using all mITT patients; Day 60/exit (confirmatory)

Secondary Outcome Measures (through Day 28 except for survival through both Day 28 and Day 60)

- 3) Time to ICU discharge using all mITT patients
- 4) Time on invasive mechanical ventilation using all mITT patients initially on invasive mechanical ventilation
- 5) Time on non-invasive ventilation using all mITT patients initially on non-invasive ventilation
- 6) Time to hospital discharge using all mITT patients
- 7) Overall survival using all mITT patients
- 8) NIAID area under the curve using all mITT patients
- 9) Multi-system organ failure using all mITT patients.

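### Time to resolution of organ failure (13.7, 14.4) has no at-risk limit, so a survivor who never has organ failure is coded as a Day 28 failure

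*Combined protocol and SAP*

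**What the plan says.** Section 13.7 (Time to Events) ends its list of secondary time-to-event outcomes with "time to discharge alive, and time to resolution of organ failure through Day 28". Section 14.4 repeats the list, ending with "time to discharge alive, and time to resolution of organ failure", and gives one set of counting rules for all of it:

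- Success and denominator: "only documented favorable events will be counted as success in the distribution construction and the denominator will include all mITT patient per treatment group".
- No event: patients "not reaching a favorable event by Day 28 will be counted as failures at Day 28".
- Death or ECMO: "Any deaths or placement on ECMO on or before Day 28, irrespective of an earlier favorable event" is a Day 28 failure.

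Two other outcomes in the list do have an at-risk limit. Section 13.7 marks both ventilation outcomes as subgroup analyses, and the hierarchy in 15.1 gives their populations: "Time on invasive mechanical ventilation using all mITT patients initially on invasive mechanical ventilation" and "Time on non-invasive ventilation using all mITT patients initially on non-invasive ventilation". No such limit is written for organ failure. Section 15.5 repeats the fixed mITT denominator for favorable events without naming organ failure.

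Section 15.8 handles organ failure differently, by counting days free of multi-system organ failure. Its organ list is sepsis, blood, brain, heart, liver and kidneys, and any one indication counts. Signs of multi-organ failure at entry are an exclusion (6.2; 9.3, item 13).

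**The concern.** A resolution endpoint has meaning only for a patient who has the condition. For respiratory failure that holds for everyone, because 9.2 requires it at entry. For the organs named in 15.8 it does not: the exclusions make it likely that many patients enter without such a failure, and some will never develop one. The 14.4 rules leave these patients in the denominator with no event they could ever have, so a good course and a death receive the same code.

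At stake is the direction of one secondary comparison. If RLF-100 prevents organ failure, fewer RLF-100 patients can score a resolution, and the curve can favor placebo while the failure-free days of 15.8 favor RLF-100. The plan would then report two organ-failure results that disagree because of coding.

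**Working it through.** The plan gives no figure for this outcome, so there is none to reproduce. The coding result in step 1 follows from the text alone. All rates in steps 3 and 4 are assumed and show direction only, except the mortality of about 50%, which is from 6.2.

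**1. Apply the rules to patients alive at Day 28 without ECMO or withdrawal.**

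| Organ-failure course | 14.4 coding | Failure-free days (15.8) |
|---|---|---|
| Never | Failure at Day 28 | No failure days, so the maximum |
| Occurs, resolution documented | Success | Fewer than the maximum |
| Occurs, not resolved by Day 28 | Failure at Day 28 | Fewer than the maximum |

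Deaths and ECMO by Day 28 are failures under 14.4 whatever the organ status. Section 13.3 (intercurrent events) and 13.4 (dropouts) do not cover the patient in the first row.

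**2. Ceiling.** Let F be the share of an arm that ever has organ failure, and r the share of those who resolve and are alive and ECMO-free at Day 28. Day 28 success is S = F × r, so S cannot exceed F.

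**3. Condition for reversal.** The outcome favors placebo when F(RLF) × r(RLF) < F(PLA) × r(PLA), that is, when r(RLF)/r(PLA) < F(PLA)/F(RLF). With assumed F and r, S is shown as RLF-100 v placebo:

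| F, RLF-100 v placebo | Break-even ratio of r | S if r = 40% v 40% | S if r = 50% v 40% | S if r = 62% v 40% |
|---|---|---|---|---|
| 10% v 20% | 20/10 = 2.00 | 4% v 8% | 5% v 8% | 6.2% v 8% |
| 20% v 30% | 30/20 = 1.50 | 8% v 12% | 10% v 12% | 12.4% v 12% |
| 30% v 40% | 40/30 = 1.33 | 12% v 16% | 15% v 16% | 18.6% v 16% |
| 40% v 50% | 50/40 = 1.25 | 16% v 20% | 20% v 20% | 24.8% v 20% |

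Equal r always reverses the direction. A large enough gain in r removes the reversal (62/40 = 1.55 exceeds every break-even except 2.00).

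**4. Disagreement with 15.8.** Take 100 patients per arm, 50 deaths in each (6.2 puts mortality at about 50%) and no ECMO. Assume that organ failure ever occurs in 20 of 50 placebo survivors and 10 of 50 RLF-100 survivors, and that 80% of these resolve.

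- Success under 14.4: 20 × 0.8 = 16 on placebo, 10 × 0.8 = 8 on RLF-100.
- Never-failed survivors coded as failures: 30 on placebo, 40 on RLF-100.
- Alive and free of organ failure at Day 28: 30 + 16 = 46 on placebo, 40 + 8 = 48 on RLF-100.
- Mean failure-free days: if failed survivors average m days in failure in both arms and the deaths contribute equally, RLF-100 gains (20 − 10) × m / 100 = 0.1m days per patient.

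**5. What the documents say about F.** There is no incidence. Section 6.2 says that deaths usually result from multisystem organ failure. If usually means more than half, then more than 0.5 × 50% = 25% of such patients die with it, so F is not small. That describes critical COVID-19 in general; the trial's exclusions could lower it.

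**The case against.** **The term may include the lung.** Sections 13.7 and 14.4 do not define organ failure, and 15.8 introduces its list with a word that need not be exhaustive. With the lung included, every patient has something to resolve and the fault disappears. This stands as a condition on the point. It is the less natural reading, because 15.8 is the only organ list for this purpose and omits the lung. It would also leave an outcome that largely duplicates the primary endpoint.

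**The all-mITT rule is already overridden elsewhere.** It covers the ventilation outcomes too, yet 13.7 and 15.1 limit those to subgroups, and 14.1 promises an SAP finalized before database lock. So the coding could still be settled. But no override is written for organ failure, and an analyst following 14.4 would use all mITT patients.

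**It looks like a leftover list item.** The outcome is absent from the Synopsis, the secondary outcomes in 8.2, the hierarchy in 15.1 and the Section 15 headings. This stands, and it sets the weight of the point.

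A reader might infer that the fault reaches a formal label claim through hierarchy item 9, multi-system organ failure. The documents do not support that: the matching analysis in 15.8, and Synopsis item 8, are failure-free days, which give a never-failed survivor full credit. A reader might also infer that reversal is expected, or of a known size. Without an incidence, the documents show only that it can happen, and step 3 includes cases where it does not.

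**Conclusion.** The point holds, and it is minor. As written, 14.4 codes a survivor who never has organ failure as a Day 28 failure on time to resolution of organ failure. That rests on one reading, that organ failure means the 15.8 list without the lung, and on no assumed rate. It caps Day 28 success at the share ever in organ failure and allows the direction to reverse under the condition in step 3. The size cannot be stated from the documents; 6.2 suggests only that the share is not small.

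The reach is one secondary outcome with no place in the testing hierarchy. The primary analysis, the sample size and hierarchy item 9 are unaffected.

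**What to change.** Delete time to resolution of organ failure from the lists in 13.7 and 14.4, and keep days free of organ failure (15.8) as the only organ-failure endpoint.

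If the outcome is kept, say which organs count, limit it to patients with organ failure at baseline, and report it descriptively only. The limit should not extend to organ failure that starts later, because that selects on a post-randomization outcome, which 14.3 rules out for the primary analysis set. Few patients are likely to qualify, since 9.3 excludes signs of multi-organ failure, cardiogenic shock, NYHA Class 3 or 4 heart failure, severe liver disease and serious neurologic disorder. Deletion is therefore the more practical choice.

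The cost is a wording change in two sections, with no new data and no effect on the sample size or the testing order. It should be made before database lock, so that it cannot be taken for a response to the results.

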## 14.5 Interim Analysis, Futility/Safety

Two pre-planned interim analyses will be conducted (n=21 initially, then an additional n=81). There will be 81% power and two-sided 5% overall Type I error to assess the primary endpoint with a total of 198 patients. The DSMB recommended that the sample size be increased to detect a smaller clinically meaningful difference for the primary efficacy endpoint (reduced from 25% to 22%).

The first interim analysis will be reviewed by the independent DSMB based on unblinded, unmasked data upon completion of 7-day data collection in the first 21 patients. DSMB meeting minutes will be recorded and provided to FDA. An unmasked/unblinded analysis will be performed for the independent DSMB in order to assess safety and efficacy. Safety determinations will entail a review of AEs and SAEs by the independent Data Safety and Monitoring Board in consultation with FDA. Based on this evaluation, the Sponsor will decide whether to permit adding additional study sites.

If the decision is made to continue the study, the next interim analysis will be performed once the next 81 patients complete the Day 28 evaluation for a safety and futility determination. As per FDA, the study will continue enrollment to 198 patients.

The details of the futility analysis follow. The futility analysis was conducted when 81 of the original 144 planned patients completed the study. If the conditional power, under the alternative hypothesis is less

than 10%, then the study will stop for futility.  $CP = \Phi(\mu\sqrt{1-t} + z_{1-p}\sqrt{\frac{t}{1-t} - \frac{z_{0.975}}{\sqrt{1-t}}})$ , where  $t = 81/144$  and  $p$  is the current corresponding one-sided p-value. The one-sided p-value to stop if the interim analysis occurs at exactly 81 patients will be 0.5949. This stop is non-binding and the DSMB will have the ability to continue if they see a positive signal in a secondary endpoint. This futility assessment will not spend any Type 1 error which will remain at 0.05.

The final sample size of 198 subjects (2:1 allocation favoring the RLF-100 group) is required to detect a 22% absolute increase in the percent with respiratory failure resolution by Day 28 for the RLF-100 group (assuming 62% success) and the SOC group (assuming 40% success) with 81% power and two-sided overall 5% Type 1 error accounting for the group sequential design using the Schoenfeld method.

The DSMB will advise regarding the favorable benefit/risk associated with early efficacy with safety.

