Dosage, Route of Administration, and Schedule:	Three escalating doses of RLF-100 (Aviptadil): 50, 100, and 150 pmol/kg/hour or placebo administered over 12 hours via IV infusion on successive days. If side effects cannot be managed with ICU protocol, dose reduced or halted.
Statistical Methods:	Primary endpoint (cumulative distribution of the time to respiratory failure resolution) with concurrent survival through Day 28 will be displayed by a lifetable through Day 28 and analyzed using a proportional hazard model analysis containing 4 pre-defined baseline covariates and randomized treatment group (primary) as well as an unstratified log rank test (secondary). Primary endpoint ascertainment requires that recovery from respiratory failure be maintained for at least 7 days without relapse. The cumulative distribution will be constructed through Day 28 with no censoring for death or withdrawal; such patients will be regarded as failures. Other time to event outcomes will be similarly analyzed with the exception of survival which will censor for any withdrawals. NIAID Score will be analyzed by carrying forward any early deaths through Day 28; other ordinal and continuous outcomes will be assessed by mixed model repeated measures through Day 28. The primary analysis will be based on the modified intent-to-treat (mITT) population to be based on all treated patients.

Sample Size Calculation:	For the primary efficacy endpoint, assuming a 40% success percent in the placebo group by Day 28 and a 62% success percent in the RLF-100 group by Day 28, for log rank test with two-sided overall 5% Type I error and 81% power, the sample size to detect a 22% absolute improvement in the percent achieving respiratory failure resolution by Day 28 (from 40% to 62%) is 198 subjects in the primary analysis group (2:1 randomization favoring the RLF-100 group). A 20% absolute advantage in the percent achieving respiratory failure resolution by Day 28 is deemed to be clinically meaningful.
Interim Analyses	An interim look for safety and futility will be conducted once the first 21 randomized subjects complete Day 7. A second interim look for safety, futility, and efficacy will be conducted once the next 81 subjects complete Day 28 but the study will not be prematurely stopped for efficacy.

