## **14. STATISTICAL ANALYSIS**

### **14.1 Statistical Design and Analyses**

All analyses will be pre-specified in a Statistical Analysis Plan to be finalized with FDA prior to database lock.

A group sequential design will be employed with one interim analyses for safety and futility (n=21) and a second interim analysis for safety and futility (n=81). At the request of FDA, the efficacy look was dropped prior to conducting the n=81 evaluation.

All calculations will be performed using SAS statistical software, version 9.3 or later, and StatXact, version 10 or later. All efficacy and safety data will be displayed in tables and listings separately for each treatment group. Post-Text TLFs will be provided in collated electronic MS Word .rtf files (i.e. table columns and rows appear in MS Word Table format).

The statistical analyses of the study will be conducted in a GCP environment (ICH E6).

There will be an independent statistical reporting group (ISRG) responsible for conducting all analyses; there will be separate unblinded biostatistician supporting the DSMB and a blinded biostatistician

responsible for any protocol modifications.

All patient data will be collected via the electronic medical record and in-house ICU telemetry systems. Dedicated research personnel will extract data to a de-identified study database for statistical analysis.

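### Does the DSMB-recommended increase from 144 to 198 patients undermine the 5% Type I error stated in Section 14.5?

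*Combined protocol and SAP*

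**What the plan says.** Section 14.5 gives the operating characteristics for the enlarged trial: "There will be 81% power and two-sided 5% overall Type I error to assess the primary endpoint with a total of 198 patients". It attributes the enlargement to the board ("The DSMB recommended that the sample size be increased to detect a smaller clinically meaningful difference") and gives the reduction from 25 to 22 points. No date or data basis accompanies this, although Section 13.5 does date the committee's advice on the endpoint, to 14 July 2020.

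On the second look, Section 14.5 says "The futility analysis was conducted when 81 of the original 144 planned patients completed the study". It puts the information fraction at 81/144 and adds "The one-sided p-value to stop if the interim analysis occurs at exactly 81 patients will be 0.5949". The rule is non-binding and is said to spend no alpha. The same section calls 198 the final size and says that enrolment continues to 198 in line with FDA.

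The purpose of that look is described in four places:

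- Synopsis: "A second interim look for safety, futility, and efficacy will be conducted once the next 81 subjects complete Day 28". The sentence goes on to exclude early stopping for efficacy.
- Section 14.1: "At the request of FDA, the efficacy look was dropped prior to conducting the n=81 evaluation".
- Section 14.5: "the next interim analysis will be performed once the next 81 patients complete the Day 28 evaluation for a safety and futility determination".
- Last sentence of Section 14.5: "The DSMB will advise regarding the favorable benefit/risk associated with early efficacy with safety".

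Section 8.3 makes expansion to 198 depend on acceptable efficacy and safety at the interim analyses, and excludes the first 21 patients from the final analysis.

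**The concern.** A conventional final test at two-sided 0.05 holds its level when the sample size is fixed independently of the treatment comparison in the patients being analysed. Here a board with access to unblinded results recommended the new size. The second look was set up on 144 patients, and the 81 patients in it remain in the final Cox analysis. If the board chose 198 after seeing their comparative result, the unadjusted test need not have 5% error. The sentence about futility spending no alpha does not cover a change of size.

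The passages that might settle the order of events do not do so. The synopsis and Section 14.1 differ on whether efficacy was part of the look. The stopping p-value fits a plan of 144, while the power statement fits 198. A reader therefore cannot confirm the 5% claim from the text alone, and that claim is what a positive primary result would rest on.

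**Working it through.** **1. The plan's own power figure.** Inputs from Section 14.5: 62% against 40%, 2:1 allocation, two-sided 5%, N = 198. (Section 14.2 prints 50% for RLF-100, but its 22-point difference and hazard ratio of 0.52 fit 62%.) I use Schoenfeld's formula with non-resolution counted as the event.

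- Hazard ratio = ln 0.62 / ln 0.40 = 0.522, which matches the stated 0.52.
- Events = 198 × (2 × 0.38 + 0.60)/3 = 89.8.
- Power = Φ(√(89.8 × 2/9) × |ln 0.522| − 1.96) = Φ(2.906 − 1.96) = 82.8%, against the stated 81%.

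The same formula for 144 patients and 25 points (65% against 40%, assuming the control rate was unchanged) gives hazard ratio 0.470, 62.4 events and power 80.2%. So the stated reason, a smaller target difference at roughly the same power, accounts for the step from 144 to 198 without any interim estimate. This does not prove that none was used.

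**2. Which plan the futility rule belongs to.** The printed formula is garbled, so I assume the standard form: CP = Φ(z√(t/(1−t)) + μ√(1−t) − 1.96/√(1−t)). A one-sided p of 0.5949 is z = −0.240.

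| t | Drift μ | Stop p for CP = 10% | CP at p = 0.5949 |
|---|---|---|---|
| 81/144 | 2.838 (81% power) | 0.568 | 8.7% |
| 81/144 | 2.954 (84% power, back-solved) | 0.5949 | 10.0% |
| 81/198 | 2.838 (81% power) | 0.864 | 28.5% |

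The rule was built on 144, as Section 14.5 says openly. The 84% power it implies is not stated in the plan.

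**3. Type I error under possible decision rules.** Let z be the interim statistic at 81 patients, with information taken as proportional to patients. Given z and a final size N, the upper-tail rejection probability under the null is 1 − Φ((1.96 − z√(81/N))/√(1 − 81/N)), and the lower tail is its mirror image. Averaging over a standard normal z gives:

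| Rule for the final size | Upper tail | Two-sided |
|---|---|---|
| Always 144, or always 198 | 2.50% | 5.00% |
| 198 if z > −0.24, else 144 | 2.47% | 5.07% |
| 198 if z > 0, else 144 | 2.44% | 5.00% |
| 198 if z > 0.5, else 144 | 2.33% | 4.84% |
| 198 if z > 1.0, else 144 | 2.19% | 4.69% |
| 198 if z > −0.24, else stop | 2.46% | 2.6% |
| 198 if z < 1.37, else 144 (worst for the upper tail) | 2.86% | 5.36% |
| Worst rule exploiting both tails | 2.86% | 5.7% |

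The direction follows from the conditional error. At z = 1.0 it is 0.0337 for 144 and 0.0429 for 198. The two are equal at about z = 1.37. At z = 2.0 they are 0.2434 and 0.1879. Enlarging helps a false positive only when the interim result is weak. Even the z < 1.37 rule gives about 3.0% (2.82% upper, 0.14% lower) if the futility stop at z = −0.24 is obeyed.

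**4. The efficacy wording.** The synopsis allows no early stop for efficacy, and Sections 14.1 and 14.5 have no efficacy look. No version gives an extra chance to reject, so the discrepancy does not affect the error rate.

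**The case for a change.** The best case for a change is that a stated error rate should be verifiable. The sponsor dated the endpoint advice and could have dated this too. The board reviews all results (Section 17.2). Section 8.3 names interim efficacy as a condition for reaching 198, and speaks of interim analyses in the plural, so it cannot be confined to the 21 excluded patients. The reference list includes a paper on sample-size modification in group sequential trials that no analysis section uses. A few sentences from existing minutes would close the question.

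The omission stands: the order of the advice and the look cannot be read from the plan. The rest carries less weight. Section 14.5 labels 144 as original and 198 as final, so the two sizes do not contradict each other. Section 14.1 makes a blinded biostatistician responsible for modifications, which is compatible with a board that may only suggest them. Section 8.3, taken at face value, is a rule to expand on good results, the direction that does not raise upper-tail error. Correcting the stopping p-value would revise a non-binding rule for a look the plan reports as already conducted. A weighted test added as a sensitivity analysis would leave the Cox test primary, and so would not change the error being questioned.

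**Conclusion.** No change to the plan follows. Inflation is not shown. The error is 5.00% if the increase did not depend on comparative results from the 81 patients. Under cut-offs representing the Section 8.3 condition it is 4.69% to 5.07% if the alternative was 144, and at most 2.6% if the alternative was stopping. The 5.36% and 5.7% figures are ceilings for enlarging after weak results, which the plan does not describe and which its stated reason, a smaller difference of interest, does not suggest.

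The missing date and data basis are a gap in the record. Section 14.5 sends the board's minutes to FDA, and Section 14.1 leaves a final SAP to be agreed with FDA before database lock, so those who must judge the 5% claim have a route to the facts. The word efficacy in the synopsis and the closing sentence of Section 14.5 are leftovers that Section 14.1 explains.

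This rests on information proportional to patients, the standard conditional-power form, and the absence of an unrecorded rule that enlarged the trial because the interim comparison was weak. Evidence of such a rule would reopen the question, with the ceilings above as its size.
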